- 2. Children diagnosed as drug-resistant epilepsy by pediatric neurologists, diagnosis was based on the ILAE 2017 criteria
- 3. Children will have got at least 3 months of combination therapy that consists of levetiracetam of topiramate with optimal of therapeutic dosages

Exclusion criteria

- 1. Non-convulsive epilepsy
- 2. Suffered from status epilepticus in the prior 3 months before the study begins
- 3. Past medical history of idiosyncrasies or severe adverse drug reactions caused by the substitution therapy that will be given

Instrument of the study

QOLCE-55 questionnaire

Once the children are enrolled, quality of life will be assessed by using validated QOLCE-55 questionnaire. It is parent-reported and self-administered questionnaire which assess quality of life children with epilepsy age 4-18 years of age. The researcher will give a detail explanation about filling the questionnaire. It has 55 questions including cognitive (22 items), emotional (17 items), social (7 items) and also physical (9 items) function. Items are rated on a five-point Likert scale, 0 = very often, 1 = fairly often, 2 = sometime, 3 = almost never, 5 = never. The composite score is the unweighted average of the four subscales, ranging from 1-100, higher score indicates better quality of life.²⁸

Diary Card

The other important thing to evaluate is subjects' adherence, seizure frequencies, and adverse drug reaction by self-reported diary card which is filled by the parents each day during the intervention phase. Besides, drug consumption compliance is also assessed by counting the tablets or powder packages during routine visits of the study.

Electronic Medical Record

Electronic Medical Record is used to collect secondary data that include demographic data, clinical characteristic, and imaging such as brain-CT or brain-MRI.

Laboratory Examination

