- current anticonvulsant(s) with doses and formulation and its side effect (if presents)
- other medications and its side effect (if presents)

- first recognized seizure date
- prior EEG and laboratory which has been performed at the baseline phase
- physical examination

Follow-up data

Follow-up data will be collected during regularly scheduled clinic visits (per 2 weeks). This information will be obtained from the participants' diary card. Important information to be collected at follow-up will include:

- physical examination
- adverse drug reaction of the substitution therapy that happen
- seizure's frequency
- type of seizure
- complaint

Outcome evaluation

- a. The difference in responders was the difference in the percentage of responders in the group that used first line OAE again as substitution therapy and those that used standard therapy. Responders are subjects who experience a decrease frequency of seizure more than or equal to 50% of the initial seizure. Frequency of seizure is the number of seizures that occur within 1 month. In previous studies, it was said that the frequency of seizures was said to have decreased significantly or was said to respond if the seizures were reduced by 50% or more from the initial seizure. ^{19, 29} Based on this, researchers will categorize the frequency of seizures into:
 - Responder: there is a decrease in the frequency of seizures by 50% or more than before
 - Non-responder: namely the frequency of seizures remains or decreases but not up to 50% of the initial seizure frequency or the frequency is more than before

Furthermore, the proportion in the form of the percentage of respondents in the two groups is calculated and differentiated, therefore it is classified into two groups:

- Different : when a significant difference is shown in difference of proportion test of the 2 unpaired groups.
- Not different: when there is no significant difference is shown in difference of proportion test of the 2 unpaired groups.

- b. Differences in quality of life: quality of life assessment using QOLCE-55 instrument. The average of each function (cognitive, emotional, social and physical functions) and the average of the total functions are assessed. This variable is categorized into:
 - Different, if there is a difference in the average quality of life
 - Not different, if there is no difference in the average quality of life
- c. Differences in electroencephalography appearance

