P1 proportion of reduced seizure on the new drug (the proportion of reduced seizure on the standard drug in addition to the minimal difference that is considered significant)= 0.7 + 0.25 = 0.95

Q1
$$1 - P1 = 1 - 0.95 = 0.5$$

P
$$(P1 + P2) / 2 = (0.95 + 0.7) / 2 = 0.825$$

Q
$$1-P = 1-0.825 = 0.175$$

In this study, it was found that the proportion of seizure reduction on standard drugs was 70%.³⁰ Therefore the equation:

$$n1 = n2 = \left(\frac{1,96\sqrt{2(0,825)(0,175)} + 0,84\sqrt{(0,95)(0,5) + (0,7)(0,3)}}{0,25}\right)^2 = 49,56 = 50$$

$$n\ 2\ groups=100$$

Based on the formula above, 100 research subjects are required. An additional of 10% from the total number of subjects are needed as there is a possibility of those dropping out, therefore a total of 110 subjects are needed in this study.

Statistical Analysis

- 1. Analysis of differences in the proportion of responders (primary outcome), differences in EEG appearance (secondary outcome) in pediatric epilepsy patients who are resistant to the combination of second line OAE between those who reused first line OAE as substitution therapy and those who used standard therapy. Data type is categorical. Data is analyzed the Chi-square statistical test, if it does not meet the requirements then an alternative test is performed, known as Fisher's multiple test. The significance level (α) is 5% and the research confidence level is 80%. If p value ≤ α is obtained, this means H0 is rejected, which means that there is a difference seen in seizure frequency between reusing first line OAE as substitution therapy and standard therapy.
- 2. Analysis of differences in the mean quality of life with an unpaired T test if the data distribution is normal or Mann-Whitney if data distribution is not normal
- 3. To assess drug effectiveness, the analysis used was the difference in actual failure between those using first line OAE as substitution therapy and those using standard therapy (primary outcome). Formula:

$$ARR = CER - EER$$

CER: the incidence of increased seizure frequency in the standard therapy group ERR: the incidence of increased seizure frequency in the group in substitution therapy with 1st line OAE The increase in seizure frequency in this study shows therapy

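### The QOLCE-55 item codes skip 4 and the stated 1-100 range does not follow from the scoring described; if applied as printed, the codes give the top response step double weight

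*Combined protocol and SAP*

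**What the plan says.** The scoring rule is in the protocol under Instrument of the study, QOLCE-55 questionnaire. The item responses are on a "five-point Likert scale, 0 = very often, 1 = fairly often, 2 = sometime, 3 = almost never, 5 = never". The structure is given as "It has 55 questions including cognitive (22 items), emotional (17 items), social (7 items) and also physical (9 items) function". The section then states: "The composite score is the unweighted average of the four subscales, ranging from 1-100, higher score indicates better quality of life".

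The score is used in Outcome evaluation, item b: "The average of each function (cognitive, emotional, social and physical functions) and the average of the total functions are assessed". Statistical Analysis, item 2, gives the test: "Analysis of differences in the mean quality of life with an unpaired T test if the data distribution is normal", with Mann-Whitney as the alternative. Quality of life is one of the between-group comparisons listed under Secondary Objectives.

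No other section restates or corrects the codes, and none says how an item code becomes a score out of 100.

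**The concern.** There are two separate inconsistencies in adjacent sentences.

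- **Codes.** Five ordered options need five codes. The printed set jumps from 3 to 5, so its steps are 1, 1, 1 and 2.
- **Range.** A lower bound of 1 does not follow from codes that start at 0 when the only stated operation is averaging. An upper bound of 100 needs a conversion that is not given.

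This is the only scoring rule in the document, and three hospitals will work from it. If it is followed literally, a one-category improvement counts twice as much at the top of the scale as anywhere else. Subscale and total means would then depend partly on where on the scale the improvements fall, and absolute scores would be lower than under even spacing. If sites instead correct the 5 on their own initiative, they may not all correct it the same way.

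**Working it through.** **Inputs, all from the QOLCE-55 section.** Codes 0, 1, 2, 3, 5; items per subscale 22, 17, 7, 9; composite = unweighted mean of four subscales; stated range 1-100. The item counts agree: 22 + 17 + 7 + 9 = 55.

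**Step 1: try to reproduce the stated range from the printed codes.**

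| Reading | Minimum | Maximum |
|---|---|---|
| Mean of item codes | 0 | 5 |
| Mean of the four subscale sums (maxima 110, 85, 35, 45) | 0 | 275/4 = 68.75 |
| Sum of 55 items | 0 | 55 × 5 = 275 |
| Percent of maximum, 100x/5 | 0 | 100 |
| 25 points per code | 0 | 125 |

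None gives 1-100. Replacing the 5 with a 4 does not repair the lower bound: 100x/4 still starts at 0. A map with an intercept, 1 + 19.8x, does run from 1 (x = 0) to 100 (x = 5), but the protocol states no such map.

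**Step 2: spacing on a 0-100 scale.** The even codes 0-4 are an assumption used for comparison; the documents do not contain them.

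| Response | Printed, 100x/5 | Even 0-4, 100x/4 | Difference |
|---|---|---|---|
| very often | 0 | 0 | 0 |
| fairly often | 20 | 25 | 5 |
| sometime | 40 | 50 | 10 |
| almost never | 60 | 75 | 15 |
| never | 100 | 100 | 0 |

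As printed, the last step is 40 points and each other step 20; with even codes every step is 25. If half the items of a subscale rise one category, the subscale gains 0.5 × 40 = 20 points at the top step and 0.5 × 20 = 10 elsewhere, against 0.5 × 25 = 12.5 with even codes.

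**Step 3: effect of one item on the composite.** An item in a subscale of k items has weight 1/(4k). Moving it from 'almost never' to 'never' changes the composite by 40/(4k) as printed and 25/(4k) with even codes:

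| Subscale | k | Printed | Even |
|---|---|---|---|
| Cognitive | 22 | 0.45 | 0.28 |
| Emotional | 17 | 0.59 | 0.37 |
| Social | 7 | 1.43 | 0.89 |
| Physical | 9 | 1.11 | 0.69 |

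**Step 4: effect on absolute means.** These response mixes are assumed for illustration, ordered from 'very often' to 'never':

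- 20/20/20/20/20%: 44.0 printed, 50.0 even.
- 10/20/30/25/15%: 46.0 printed, 53.75 even.
- 5/10/20/30/35%: 63.0 printed, 70.0 even.

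The printed codes give means 6 to 8 points lower.

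**Step 5: does the rank test remove the problem?** Take two children on the 22-item cognitive subscale. Child A answers 'almost never' throughout. Child B answers 'never' to 10 items and 'sometime' to 12.

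- Printed: A = 60.0; B = (10 × 100 + 12 × 40)/22 = 1480/22 = 67.3.
- Even: A = 75.0; B = (10 × 100 + 12 × 50)/22 = 1600/22 = 72.7.

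The order reverses. Ranks are taken on averaged items, so Mann-Whitney is not immune.

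**The case against.** The strongest reply is that the 5 is a misprint in a short summary of a validated, cited instrument, and that sites will score from the instrument itself. That may be so; the documents cannot settle it. The harm is therefore conditional on the codes being used as printed. It is still unsafe to assume that slips are caught before use. In the Sample size section, 1 − 0.95 is printed as 0.5 and carried into the formula. With 0.5 the formula gives about 48.9, near the stated 49.56; with 0.05 it gives about 35.0.

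The second reply is that the effect on the between-arm test is small. This largely stands for a broad shift in responses. In a simulation with 50 children per arm, a one-factor latent trait, inter-item correlation 0.2 or 0.4, low, middle or high baselines and a uniform shift of 0.55 latent SD, composites under printed and even codes correlated at 0.995 to 0.998. Power differed by about 2 percentage points at most. Effects concentrated in the top category could differ more. The range misstatement alone changes no p-value, because the scales concerned differ only by a linear rescaling.

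Three stronger readings are tempting and are not supported:

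- A reader might infer that the trial's quality-of-life score is already distorted. The documents show a faulty rule; they do not show that it was applied.
- A reader might infer that 1-100 is mathematically impossible. It fails under averaging or proportional rescaling, but an unstated intercept would produce it.
- A reader might infer bias toward one arm. Both arms are scored by the same rule, so the codes alone favour neither.

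It would also go too far to assert that 0-4 is the intended coding. A printed 5 and a lower bound of 1 could equally be remnants of 1-5 coding.

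**Conclusion.** The point holds in this limited form. The printed codes are not evenly spaced, and the stated range does not follow from the stated rule; both can be seen on the page without outside sources. If the codes are applied literally, the top step has twice the weight of any other (40 against 20 points). An individual item is scored 0 to 15 points below its evenly spaced value, and the order of children can change. The comparison values assume evenly spaced codes rescaled to 0-100.

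The consequence is confined to the spacing and absolute level of a secondary outcome. The primary responder analysis and the sample size do not use this score. It should be corrected because it is the only scoring rule the plan gives and the correction is cheap.

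**What to change.** 1. Before data entry, check the item codes against the instrument's own scoring instructions.
2. State one evenly spaced set of five codes in the protocol. If the instructions confirm it, this could be 0-4 with each item multiplied by 25.
3. State the conversion from item code to the 100-point scale, then averaging of items within each subscale (22, 17, 7 and 9 items), then the unweighted average of the four subscales.
4. State the range that follows, which is 0-100 under that example coding.
5. Rescore any form already entered with the printed codes, and use the same scoring sheet at all three hospitals.

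The cost is one line in the protocol and one in the scoring sheet. No additional data are needed.

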This protocol is intended for a multicenter open label experimental, randomized controlled trial on the efficacy and safety of using first line AEDs as substitution therapy in childhood drug-resistant epilepsy. It will prospectively follow 100 children up during 14 weeks that consist of baseline, intervention, and post-intervention phases. While the intervention consists of 6 steps, as described at the Figure 1 below.

[figure not shown]

Figure 1. Timeline of the intervention phases

The study will be conducted at pediatric outpatient clinic of 3 referral hospitals in Jakarta, Cipto Mangunkusumo Hospital, Harapan Kita Hospital and Fatmawati Hospital. Children who are diagnosed with drug-resistant epilepsy receiving levetiracetam or topiramate will be enrolled in the study. Enrollment begins as soon as the research ethics committee approval is obtained from The Ethics Committee of The Faculty of Medicine, University of Indonesia-Cipto Mangunkusumo Hospital. The study will be closed after the last recruited patient has been followed up for the required 14 weeks.

All recruited children will be examined for monitoring at the hospital where the intervention is initiated. To avoid selection bias, all patients who met the inclusion criteria are divided into two groups, the intervention and control groups. Prospective participants and their parents will be provided with information related to the study. Patients will then fill out an information sheet containing demographic data, comorbidities, developmental history, school history, history of drug consumption, as well as history of seizures and patient complaints. All the data will be extracted and recorded on the case report form. Patients and their parents should be informed that participation is voluntary and they are free to withdraw from the study at any time. They should also be informed that refusal to participate or withdraw from the study will not affect the quality of treatment received. In the event of their withdrawal, it will be explained that the data collected so far is irrevocable, and we will seek consent to use such data in the final analysis if necessary.

Study procedure

Study procedures are depicted in Figure 2. The patients who are eligible for the study and have given their consents, will be enrolled, divided into 2 groups, the intervention and control, then start the 3-day baseline phase. In this phase, data such as demographic, clinical characteristic

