including seizure frequency, seizure type, seizure onset, medication history, family history of seizure, and also developmental stages, will be recorded from electronic medical record. Besides, the CT-scan or MRI are also collected from the same source. After that, their quality of life will be assessed by QOLCE-55 validated questionnaire through self-guided report. Furthermore, the laboratory investigation and EEG will be performed.

The next phase is intervention phase, started from initial step and ended by the maintenance of new combination therapy, which takes with overall 12 weeks. Initially, the substitution drugs with each initial dose are consumed. The drugs consist of valproic acid for the generalized and carbamazepine for focal epilepsies. On the other hand, the control group will take lamotrigine or clobazam for generalized and oxcarbazepine for focal ones. The phase continuous to titration dose, in which, the dose is raised gradually until it causes 50% of seizure reduction, and the next step is maintained the dose for about 2 weeks.

The following is tapering-off and after that stopping the substituted drug, levetiracetam or topiramate, which is determined by considering individual condition. Yet, if the seizures increase more than one and a half time of the previous frequency during the phases, the intervention will be ended immediately. On the contrary, if the condition is better, then the children go to the maintenance of new combination, that is the substitution drug and the old drugs in which the seizures do not go up or even better keep going down. The children who complete all of the phases are categorized as responder. In case if the intervention is ended, the subjects will be given the former combination therapy with adjusted doses in order to decrease the seizures until reaching the pre-intervention condition. The subjects are categorized as non-responder, and will be dropped-out. The other criteria of drop-out are resignation, non-compliance of study procedure, and death in term of other causal not related to the study. While in term of lost to follow-up, is intended for those who do not attend the study without any possible reasons.

[figure not shown]

Figure 2. flow-chart of the study

Maintenance the dose of the new combination therapy that consist of the new drug and

Maintenance

old drug after stopping the substituted drug

Inclusion criteria

- 1. Children age at 1 18 years old

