The test is performed in hospitals' laboratory where the study take place and is done twice, at the baseline and post intervention phase. The order of the blood test consists of complete blood test, liver function test including alanine and aspartate transaminase, kidney function test including urea and creatinine, and also blood electrolyte that consist of natrium, kalium and calcium. The laboratory professional takes the blood from vein of the arm. The subjects are seated or lying down, accompanied by the parents, while for the younger children, they seat on his/her parents' lap or position that make them feel comfortable. Older children may be asked to make a fist and then will be tied by a rubber band around his/her arms. After that, the needle is inserted the needle until the blood is drawn. The laboratory worker will take the needle since the amount of blood is enough and puts an adhesive bandage over the site. The next step is analyzes of the sample and the result will be issued for about 1-2 days both printed or provided on the electronic medical record.

Electroencephalography Examination

The EEG examination is operated two times, at the baseline and post intervention phase, with high density machine (Caldwell Easy III) is done twice, pre- and post-intervention. The machine will operate for about 45 minutes including 5 minutes each for eye-open and eye-close in every subjects. Beginning with acquisition, EEG recordings use standard parameter to analyze brain activity at various frequencies to gain good quality and artefact-free result. The printed results of the EEG is available for about 4-7 days after the examination.

Data collection

All relevant data will be recorded, by nominated member(s) of the research team, on a case report form (CRF). Each participant will have a CRF and be assigned a unique identification number.

Baseline data

At entry into the study, the following baseline information will be recorded in the CRF:

- unique patient identification number contact telephone number and/or email address
- date of entry into the study
- eligibility for study entry based on inclusion/exclusion criteria
- age at study entry, in years and months
- gender
- weight and height
- seizure type (eg, generalized tonic clonic, absence, myoclonic and partial)
- the age at diagnosis and duration of epilepsy
- seizure frequency or average number of seizures per month

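### The primary 50% reduction compares a diary count with a baseline from another, loosely specified source, so it cannot be assumed to be a true 50% reduction

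*Combined protocol and SAP*

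**What the plan says.** Outcome evaluation, item a, sets the primary rule: "Responders are subjects who experience a decrease frequency of seizure more than or equal to 50% of the initial seizure". It gives the unit as well: "Frequency of seizure is the number of seizures that occur within 1 month". It does not name the follow-up month to be used.

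**Baseline side.** Under Study procedure, children are enrolled, divided into the two groups, and then "start the 3-day baseline phase". In that phase, data "including seizure frequency, seizure type, seizure onset, medication history, family history of seizure, and also developmental stages, will be recorded from electronic medical record". The Baseline data list asks for "seizure frequency or average number of seizures per month", with no look-back period. Separately, Study Design has families complete an information sheet that covers "history of seizures and patient complaints", and this also goes onto the case report form.

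**Follow-up side.** Follow-up data lists seizure frequency among the items collected every 2 weeks and says: "This information will be obtained from the participants' diary card". Under Instrument of the study, Diary Card, this is a "self-reported diary card which is filled by the parents each day during the intervention phase". No diary before the intervention phase is described.

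**A second responder rule.** Study procedure also classes children who complete all phases as responders, without reference to a percentage fall.

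**The concern.** A percentage change means what it says only if both counts come from the same kind of measurement. Here the later count is a daily parent record. The stated source of the initial count is a retrospective chart average over an unstated period. If the chart misses seizures that a diary would catch, children need more than a true 50% fall to qualify. If the chart overstates them, less is enough.

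Timing adds a second problem. The trial is open label and the baseline phase follows division into groups, so whoever picks the monthly figure from the record can know the child's arm. With no look-back period and two possible sources, there is room for choice.

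At stake are the meaning of the primary responder percentages and the power of their comparison. If the choice differs by arm, the validity of the comparison is at stake too. The initial frequency is also one of the factors to be analysed for seizure reduction, and the 50% titration target reads as if it used the same baseline.

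**Working it through.** **1. The plan's own figure.** The plan gives no figure for agreement between chart and diary. Its only number tied to this outcome is the sample size for 70% against 95% responders. With the printed inputs (1.96, 0.84, P = 0.825, Q = 0.175, Q1 = 0.5):

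- 1.96 × √(2 × 0.825 × 0.175) = 1.053
- 0.84 × √(0.95 × 0.5 + 0.7 × 0.3) = 0.695
- ((1.053 + 0.695) / 0.25)² = 48.9, against 49.56 printed, rounded to 50

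This agrees to within about one child per group. It uses Q1 = 0.5 where 1 − 0.95 = 0.05; with 0.05 the formula gives 35.0. That is a separate matter. What is needed below is 50 per group and the 70% and 95% rates.

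**2. The two sides of the ratio.**

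| | Initial frequency | Follow-up frequency |
|---|---|---|
| Stated source | Medical record; a family seizure history is also collected | Parent diary card |
| Method | Retrospective, average per month | Daily, prospective |
| Window | Not stated | 1 month, which month not stated |
| Timing | After division into groups | Intervention phase |

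**3. What an observed 50% fall requires.** Let r be the baseline source's count divided by the count a diary would have given for the same period. r is an assumption; the documents give no value.

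- Observed ratio = follow-up / (r × diary-equivalent baseline)
- Observed ratio ≤ 0.5 means true ratio ≤ 0.5r, so the true reduction needed is 1 − 0.5r

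| r | True reduction needed |
|---|---|
| 0.5 | 75% |
| 0.7 | 65% |
| 0.9 | 55% |
| 1.0 | 50% |
| 1.25 | 37.5% |

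Example: a diary would have shown 40 seizures a month. At r = 0.7 the chart shows 28, the child must reach 14, and the true fall is 26/40 = 65%. At r = 1.25 the chart shows 50, the child must reach 25, and the true fall is 15/40 = 37.5%.

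**4. Same r in both arms.** Assume that each child's follow-up/baseline ratio is lognormal with log-SD s, anchored so that r = 1 gives 70% and 95%. The observed rate is then Φ(Φ⁻¹(p) + ln r / s). Power at n = 50 per group, two-sided 5%, is Φ[(|p1 − p2| − 1.96√(2p̄(1 − p̄)/n)) / √((p1q1 + p2q2)/n)].

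| r | Rates, s = 0.5 | Power | Rates, s = 1.0 | Power |
|---|---|---|---|---|
| 0.8 | 53.1% / 88.5% | 98% | 61.8% / 92.2% | 96% |
| 1.0 | 70% / 95% | 92% | 70% / 95% | 92% |
| 1.25 | 83.4% / 98.2% | 73% | 77.3% / 96.9% | 84.5% |
| 1.5 | 90.9% / 99.3% | 49% | 82.4% / 98.0% | 75% |

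Power falls when r is above 1, because both rates approach the ceiling, and rises when r is 0.8. If the arms truly do not differ, an equal r moves both rates identically and no difference appears.

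**5. Different r by arm.** Take a true rate of 70% in both arms and a 1.25-fold shift in one arm only. The observed rates are 83.4% against 70% (s = 0.5) or 77.3% against 70% (s = 1.0). The chance of a significant result in that direction is about 35% or 13%, against a nominal 2.5%. This shows sensitivity; the documents do not say that such a shift will occur.

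**6. The 3-day phase as a substitute.** The plan does not propose counting seizures in these days, and they could not supply a monthly figure. Under a Poisson assumption, a child with 4 seizures per 30 days has probability exp(−4 × 3/30) = 67% of none.

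**The case against.** The strongest reply is that nothing here is shown to be wrong, only unspecified. Most of its parts stand in some measure.

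- **No capture rates.** A reader might infer that the observed threshold is definitely not a 50% reduction. The documents do not support that: it would follow only if chart and diary capture seizures differently, and they give no evidence on this either way. For r below 1 the illustrative model shows power rising.
- **The chart is not the only source.** The family's seizure history could serve as the initial frequency. This stands, so the denominator cannot be called purely chart-based. It does not remove the problem: no monthly count, window or seizure definition is given for that history, and it is recall, not a daily record.
- **No false difference from a common error.** Correct, as step 4 shows.
- **Chart entries predate allocation.** Also true. Only their extraction could be influenced. But with no look-back period and an unnamed source, extraction involves choice.
- **Not every rule uses this baseline.** A reader might infer that stopping and failure also rest on it. The stopping rule refers to a previous frequency that is not defined, and the failure analysis counts increased frequency without naming a reference. Neither need be this baseline.
- **Planning values.** A reader might infer that the 70% and 95% rates are thereby invalid. How the source of the 70% measured its baseline is not stated, so this cannot be checked.

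**Conclusion.** The point holds as a measurement and specification weakness in the primary outcome. Followed as written, the plan puts two instruments into the 50% ratio, leaves the initial source and both windows open, and records the baseline when the arm can be known. The true reduction needed is 1 − 0.5r, which equals 50% only at r = 1; across an assumed r of 0.5 to 1.25 it runs from 75% to 37.5%. Neither direction nor size can be established from the documents.

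Two consequences should be kept apart. A common r alters responder rates and power without creating a false difference. Bias between arms needs r to differ by arm; open-label extraction after division makes that possible, but the documents do not show that it happens. The power and false-positive figures rest on the lognormal model and its assumed spread. The plan should correct this before enrolment, because a baseline recorded before allocation cannot be recovered later.

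**What to change.** 1. **Baseline.** Before allocation, have the parent complete, on the diary form, a structured count of seizures in the previous 28 days, using the diary's seizure definitions. Name this as the initial frequency in both arms, in place of the chart average. The chart figure can stay on the case report form as description.
2. **Follow-up.** Compare it with a named 28-day diary window at the end of follow-up. As the card is kept during the intervention phase, the last 28 days of that phase would suit.
3. **Zero counts.** State how a child with no seizures in the 28 days is handled. The eligibility criteria set no minimum frequency; at an assumed 1 seizure per 30 days, the Poisson chance of none is exp(−28/30) = 39%.
4. **Responder definition.** Reconcile the completion rule in Study procedure with the 50% rule in Outcome evaluation, item a.

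**Cost.** One more use of an existing form, with no delay and no extra visit. The downside is that the baseline is still recall, so the two instruments are brought closer but not made identical.

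**Optional.** A prospective 28-day diary before allocation is better where recruitment allows, and can fall within the 3 months of combination therapy already required. It is a trade-off: November 2022 to April 2023 is about 26 weeks, 14 weeks of follow-up leave about 12 for recruitment, and a 4-week run-in could take a third of that.
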